### **Change from baseline in endpoints derived from the 7-9-7-point SMPG profile to 16 weeks after randomisation**

In general, analyses will be based on the entire 7-9-7-point SMPG profile.

Protocol  
Trial ID: NN1218-4357  
UTN: U1111-1197-8289

CONFIDENTIAL

Date:  
Version:  
Status:  
Page:

30 November 2020  
5.0  
Final  
84 of 105

Novo Nordisk

PPG and PPG increments based on the 7-9-7-point SMPG profiles will be derived separately for PG measurements made 1 hour after the meal. In the following section this distinction will be considered implicit and without further explanation.

Pre-prandial PG and PPG will be recorded by the subjects as part of the 7-9-7-point SMPG profile prior to three defined visits. Individual mean mealtime PPG (post-breakfast, post-lunch, post-main evening meal) will be derived from the three profiles. Overall mean PPG will be derived from the individual derived mealtime PPG values.

PPG increment for each meal (breakfast, lunch, main evening meal) will be derived from the 7-9-7-point SMPG profile as the difference between PPG values and the PG value before meal in each separate profile. The mean of the derived increments will then be calculated separately for each meal. Mean 1-hour PPG increments over all meals will be derived as the mean of all corresponding mean meal increments.

- Change from baseline in mean of the 7-9-7-point SMPG profile

The mean of the 7-9-7-point SMPG profile is defined as the area under the curve (AUC) profile divided by the measurement time, and is calculated using the linear trapezoidal technique.

Change from baseline in the mean of the 7-9-7-point SMPG profile 16 weeks after randomisation will be analysed based on all planned post baseline measurements until or at 16 weeks after randomisation using a model similar to the primary analysis except with the corresponding baseline value as covariate.

- Change from baseline in 1-hour PPG and PPG increment (mean, breakfast, lunch and main evening meal)

Change from baseline in 1-hour PPG and PPG increment endpoints 16 weeks after randomisation for mean over all three meals and the individual meals will be analysed separately based on all planned post baseline measurements until or at 16 weeks after randomisation using a model similar to the primary analysis except with the corresponding baseline value as covariate.

- Fluctuation in 7-9-7-point SMPG profile

The fluctuation in the 7-9-7-point SMPG profile is defined as:

$$\frac{1}{T} \int_0^T |PG(t) - \bar{PG}| dt$$

Protocol  
Trial ID: NN1218-4357  
UTN: U1111-1197-8289

CONFIDENTIAL

Date:  
Version:  
Status:  
Page:

30 November 2020  
5.0  
Final  
85 of 105

Novo Nordisk

where  $T$ ,  $PG(t)$  and  $\bar{PG}$  denotes the length of the profile, the  $PG$  value at time  $t$  and the mean of the profile, respectively. It will be calculated using the linear trapezoidal technique.

Fluctuation in the 7-9-7-point SMPG profile will be logarithmically transformed and analysed based on all planned post baseline measurements until or at 16 weeks after randomisation using a model similar to the primary analysis except with the corresponding log-transformed baseline value as covariate. Estimated treatment means and the estimated treatment differences with corresponding 95% CI will be back-transformed to the original scale, resulting in estimated geometric means, a treatment ration and a 95% CI for the treatment ratio.

**If a subject achieves PPG target (based on overall mean of daily PPG measurements in 7-9-7-point SMPG profile) 16 weeks after randomisation:**

**Overall PPG (1-hour)  $\leq 7.8$  mmol/L**

A dichotomous (responder/non-responder) endpoint will be defined based on whether a subject has reached an overall mean 1-hour PPG  $\leq 7.8$  mmol/L [140 mg/dL] 16 weeks after randomisation, where PPG is derived from the 7-9-7-point SMPG profile.

This responder endpoint will be analysed based on a logistic regression model using treatment and stratification (T1DM/T2DM) as factors, and baseline overall mean 1-hour PPG as covariate. In the analysis, subjects who prematurely discontinue randomised treatment will be included as non-responders.

**Overall PPG (1-hour)  $\leq 7.8$  mmol/L without severe hypoglycaemia**

A dichotomous (responder/non-responder) endpoint will be defined based on whether a subject has reached an overall 1-hour PPG  $\leq 7.8$  mmol/L [140 mg/dL] 16 weeks after randomisation without any treatment emergent severe hypoglycaemic episodes.

This responder endpoint will be analysed based on a logistic regression model using treatment and stratification (T1DM/T2DM) as factors, and baseline overall mean 1-hour PPG as covariate. In the analysis, subjects who prematurely discontinue randomised treatment will be included as non-responders.

**Insulin dose (Units/day and Units/kg/day; total basal, total bolus, and individual meal insulin dose) 16 weeks after randomisation**

The insulin doses will be summarised descriptively by treatment week according to regimen, by meal type in units and units/kg (separately for each mealtime dose). Insulin doses will be summarised using the safety analysis set.

Protocol  
Trial ID: NN1218-4357  
UTN: U1111-1197-8289

CONFIDENTIAL

Date:  
Version:  
Status:  
Page:

30 November 2020  
5.0  
Final  
86 of 105

Novo Nordisk

## Lipids-lipoproteins profile 16 weeks after randomisation

Lipid endpoints (total cholesterol, HDL cholesterol, LDL cholesterol and triglyceride) will be logarithmically transformed and analysed separately based on all planned post baseline measurements until or at 16 weeks after randomisation using a model similar to the primary analysis except with the corresponding log-transformed baseline as covariate. Estimated treatment means and the estimated treatment difference with corresponding 95% CI will be back-transformed to the original scale, resulting in estimated geometric means, a treatment ratio and a 95% CI for the treatment ratio.

### 17.4.1.2 Safety endpoints

In terms of AEs, as a minimum, SAEs will be tabulated.

#### Number of treatment emergent adverse events

AEs will be coded using the Medical Dictionary for Regulatory Activities (MedDRA). AEs will be presented based on system organ class and preferred terms.

A Treatment Emergent Adverse Event (TEAE) is defined as an event that has an onset date on or after the first day of exposure to randomised treatment, and no later than seven days after the last day of exposure to randomised treatment.

TEAEs are summarised descriptively, whereas AEs not defined as treatment emergent are presented in listings, including AEs reported in the 30-day follow-up period. The summaries of TEAEs are made displaying the number of subjects with at least one event, the percentage of subjects with at least one event, the number of events and the event rate per 100 subject years of exposure. These summaries are done by seriousness, severity, relation to insulin treatment, relation to technical complaint, premature treatment discontinuation due to AEs, AEs leading to withdrawal from trial and outcome.

Furthermore, summary tables based on system organ class and preferred terms are made for:

- All TEAEs
- Serious TEAEs
- Possibly and probably related TEAEs
- Severe TEAEs
- TEAEs with preferred term that are experienced by at least 5% of the subjects in any treatment arm or by at least 5% of all subjects

For AEs where additional information is recorded, this will be listed.

AEs occurring during the run-in period are considered non-treatment emergent and will be summarised separately.

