### **12.2 Reporting of adverse events**

All events meeting the definition of an AE must be collected and reported. This includes events from the first trial-related activity after the subject has signed the informed consent until the end of the post-treatment follow-up period (FU2). For subjects discontinuing trial product prematurely, only SAEs should be reported between FU2 and end of trial (V26B). The events must be recorded in the applicable eCRF forms in a timely manner, see timelines below and [Figure 12-1](#).

During each contact with the trial site staff, the subject must be asked about AEs and technical complaints, for example by asking: "Have you experienced any problems since the last contact?"

All AEs, either observed by the investigator or subject, must be reported by the investigator and evaluated.

All AEs must be recorded by the investigator on an AE form. The investigator should report the diagnosis, if available. If no diagnosis is available, the investigator should record each sign and symptom as individual AEs using separate AE forms.

For SAEs, a safety information form must be completed in addition to the AE form. If several symptoms or diagnoses occur as part of the same clinical picture, one safety information form can be used to describe all the SAEs.

For all non-serious AEs, the applicable forms should be signed when the event is resolved or at the end of the trial at the latest.

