### **12.3 Follow-up of adverse events**

The investigator must record follow-up information by updating the forms in the eCRF.

Follow-up information must be reported to Novo Nordisk according to the following:

- SAEs:** All SAEs must be followed until the outcome of the event is “recovered/resolved”, “recovered/resolved with sequelae” or “fatal”, and until all queries have been resolved. Cases of chronic conditions, cancer or AEs ongoing at time of death (where death is due to another AE) may be closed with the outcome “recovering/resolving” or “not recovered/not resolved”. Cases can be closed with the outcome of “recovering/resolving” when the subject has completed the follow-up period and is expected by the investigator to recover.

The SAE follow-up information should only include new (e.g. corrections or additional) information and must be reported **within 24 hours** of the investigator’s first knowledge of the information. This is also the case for previously non-serious AEs which subsequently become SAEs.

- Non-serious AEs:** Non-serious AEs must be followed until the outcome of the event is “recovering/resolving”, “recovered/resolved” or “recovered/resolved with sequelae” or until the end of the follow-up period stated in the protocol, whichever comes first, and until all queries related to these AEs have been resolved. Cases of chronic conditions, cancer or AEs ongoing at time of death (where death is due to another AE) may be closed with the outcome “recovering/resolving” or “not recovered/not resolved”. Cases can be closed with the outcome

Protocol  
Trial ID: NN1218-4357  
UTN: U1111-1197-8289

CONFIDENTIAL

Date:  
Version:  
Status:  
Page:

30 November 2020  
5.0  
Final  
71 of 105

Novo Nordisk

of “recovering/resolving” when the subject has completed the follow-up period and is expected by the investigator to recover.

The investigator must ensure that the recording of the worst case severity and seriousness of an event is kept throughout the trial. A worsening of an unresolved AE must be reported as follow up with re-assessment of severity and/or seriousness of the event.

Queries or follow-up requests from Novo Nordisk must be responded to **within 14 calendar days** from the date of receipt of the request, unless otherwise specified in the follow-up request.

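### The onset-only TEAE definition leaves out of the by-arm tables an AE that starts in the run-in, is still open at V10, and worsens on randomised treatment

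*Protocol*

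**What the plan says.** Protocol 17.4.1.2 and SAP 4.4.1.2 give the same definition. An event is treatment emergent by its onset date: "A Treatment Emergent Adverse Event (TEAE) is defined as an event that has an onset date on or after the first day of exposure". Exposure here means the randomised product, and the window closes "no later than seven days after the last day of exposure to randomised treatment". Neither document has a clause for an event that was already present and then worsened. Both add: "AEs occurring during the run-in period are considered non-treatment emergent and will be summarised separately". SAP 4.5 reports no change to the protocol analyses, so the SAP adds nothing on this.

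AE collection starts well before randomisation. Protocol 12.2 states: "This includes events from the first trial-related activity after the subject has signed the informed consent". An AE that arises during the 8-week run-in can therefore still be open at V10.

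Protocol 12.3 says how later deterioration is recorded: "A worsening of an unresolved AE must be reported as follow up with re-assessment of severity and/or seriousness of the event". It also requires that "the recording of the worst case severity and seriousness of an event is kept throughout the trial". For the 24-hour deadline on SAE follow-up information, it adds: "This is also the case for previously non-serious AEs which subsequently become SAEs".

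**The concern.** Comparing safety is the trial's secondary objective (Protocol 4.1.2). Numbers of TEAEs and of treatment emergent injection site reactions are named endpoints (4.2.2.2). The summaries by seriousness, severity, relationship, discontinuation and withdrawal in 17.4.1.2 are all summaries of TEAEs, so an event that fails the definition is missing from every one of them.

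The run-in is on trial insulin, and its bolus component is open-label NovoRapid, the comparator molecule and formulation (5.3). At V10 only subjects allocated to faster aspart change formulation, to one with two added excipients (3.1.3). A reaction that was mild on NovoRapid and worsened after that change is what a safety comparison should be able to count. An onset-only rule combined with a follow-up-only record cannot count it.

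**Working it through.** The documents give no figure that rests on the TEAE definition, so there is nothing of the plan's own to reproduce. The check is a reading of the rules side by side.

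1. **Entry to the TEAE tables** (17.4.1.2, SAP 4.4.1.2): the onset date must lie between the first randomised dose and seven days after the last. No other route is given.
2. **Status of run-in AEs** (same sections): non-treatment emergent, with no exception for later change.
3. **Recording of change** (12.3): worsening of an unresolved AE updates the existing AE, with the worst grade kept. The section does not mention onset date. A follow-up to an existing record supplies no new one, so retention of the first date is the natural reading, but it is inferred.

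Take an AE that starts in the run-in as mild and non-serious, is unresolved at V10, and becomes severe or serious in week 4 of randomised treatment. By step 3 the same record is updated. By steps 1 and 2 its onset precedes randomised treatment, so it is absent from the tables of all, serious, severe and related TEAEs.

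Neighbouring rules that might bring the event back:

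- **Concomitant illness (8.2.4, 12.1.1).** Clinically significant worsening is a reportable AE. The category covers illness present at V1 or found before exposure to trial product. Run-in insulins are trial products (8.1.2, Table 9-1), so an AE arising on them is outside it.
- **Eye findings (8.4.3).** Relevant findings before randomisation are recorded as concomitant illness or medical history, so later worsening can be a new AE. These are not affected.
- **Resolved and recurring AEs.** The follow-up rule applies to unresolved AEs only, so a recurrence can enter with its own onset.
- **Hypoglycaemic episodes.** They are recorded episode by episode and have their own treatment emergent definition. Not affected.
- **Safety assessments (8.4).** Clinically significant worsening from baseline is to be reported as an AE, and 4.2 sets baseline at V10. For an assessment finding already open as an AE, this could mean a new AE, whereas 12.3 means follow-up. Neither section is given precedence.
- **Opening line of the safety analysis (17.4.1.2).** SAEs are to be tabulated as a minimum, not expressly only treatment emergent ones. This does not make a run-in-onset SAE treatment emergent.

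What remains is an AE that starts in the run-in and stays open, other than an assessment finding that a site reports afresh under 8.4.

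**Size.** No AE rate, duration or worsening share is given. As an illustration only, assume 2 to 4 AEs per subject-year, a mean duration d of 2 to 6 weeks (exponential), and 5 to 10% of open AEs worsening. The expected number open at V10 per subject is (rate/52) × d × (1 − exp(−8/d)).

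- Rate 2, d = 2: 0.076; d = 6: 0.170
- Rate 4, d = 2: 0.151; d = 6: 0.340

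Times 300 randomised, this is about 23 to 102 open AEs. At the ends of the range, 23 × 5% ≈ 1 and 102 × 10% ≈ 10 events. Every input is assumed, so this shows only why the number is probably small. It is not an estimate.

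**The case against.** The strongest reply is that the definition is prespecified, identical in both documents and applied equally to two blinded arms, and that the events are not lost. AEs that are not treatment emergent are listed. An upgrade to serious must be reported within 24 hours. The primary reason for stopping trial product is recorded whatever the AE's onset (8.1.9). TEAEs are summarised descriptively, with no test or margin that could be passed wrongly. All of this stands. It limits the point to the counts in the by-arm tables.

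The objector can also say that 12.3 is silent on onset date and that 8.4 may generate a new AE. Both are true. The first makes the conclusion an inference. The second shows two rules that need reconciling, because sites could record the same deterioration in two ways.

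Some stronger conclusions are tempting but not supported:

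- A reader might infer that worsening can never reach the TEAE tables. The routes above for concomitant illness, eye findings, recurrence and possibly assessment findings show otherwise.
- A reader might infer a bias towards finding no safety difference. The TEAE comparison changes only if worsening of run-in AEs differs by arm, and nothing in the documents shows that it does. The run-in summary covers a period when everyone took NovoRapid, so a misplaced grade there is not an error in the arm comparison.
- A reader might infer that the run-in summary will show post-randomisation grades. That could happen, because the worst case is kept, but the plan does not say that this summary is by severity or which grade it uses.

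**Conclusion.** The point holds in limited form. On the natural reading of 12.3 with 17.4.1.2 and SAP 4.4.1.2, an AE that begins in the run-in, is open at V10, and increases in severity or becomes serious on randomised treatment is not counted in the TEAE tables by arm. This rests on the inference that follow-up leaves the onset date unchanged. The number of such events cannot be estimated from the documents and is probably small. Reporting and listing of the events are intact, and the direction of any effect on the comparison is unknown. The case for a change is that these few events are ones that deteriorated on randomised treatment, and the current rule excludes them from the comparison meant to serve the secondary objective. This is a worthwhile low-cost improvement, not a threat to the trial's conclusions.

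**What to change.** - **Protocol 17.4.1.2 and SAP 4.4.1.2:** keep the onset criterion and add that an AE with earlier onset is also treatment emergent if it increases in severity or becomes serious from the first day of randomised treatment to seven days after the last day. State that the same rule applies to injection site reactions.
- **Protocol 12.3:** keep one record per event, but capture the date of worsening for any AE open at the first randomised dose. Opening a second AE instead would split one clinical event across the run-in and TEAE counts.
- **Run-in summary:** if it is shown by severity or seriousness, use the grade reached before the first randomised dose.
- **Protocol 8.4 and 12.3:** reconcile them, so that an assessment finding already open as an AE is handled in one way.

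The cost is a sentence in each document, one extra date field, and a slightly higher TEAE count. A reader might expect the dates for events already entered to be recoverable from the eCRF audit trail. Section 13.1 says the trail holds the date and time of entry, which is not the date of clinical worsening, so those events would need site queries.

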## Number of treatment emergent injection site reactions

Treatment emergent injection site reactions occurring during the trial will be summarised and listed.

### Classification of Hypoglycaemia

Treatment emergent: hypoglycaemic episodes will be defined as treatment emergent if the onset of the episode occurs on or after the first day of exposure to randomised treatment, and no later than one day after the last day of exposure to randomised treatment.

Nocturnal hypoglycaemic episodes: episodes occurring between 00:01 and 05.59 both inclusive.

[figure not shown]
Hypoglycaemic episodes are classified according to the Novo Nordisk classification of hypoglycaemia (see [Figure 17-1](#)) and the ADA classification of hypoglycaemia (see [Figure 17-2](#)).

### Novo Nordisk classification of hypoglycaemia

In normal physiology, symptoms of hypoglycaemia occur below a PG level of 3.1 mmol/L (56 mg/dL). Therefore, Novo Nordisk has included hypoglycaemia with PG levels below this cut-off point in the definition of BG confirmed hypoglycaemia.

Novo Nordisk uses the following classification (see [Figure 17-1](#)) in addition to the ADA classification:

- Severe hypoglycaemia according to the ADA classification.
- Severe or BG confirmed hypoglycaemia: An episode that is severe according to the ADA classification or BG confirmed by a PG value <3.1 mmol/L (56 mg/dL) **with or without** symptoms consistent with hypoglycaemia.

[figure not shown]
Note: Glucose measurements are performed with capillary blood calibrated to plasma equivalent glucose values

BG: blood glucose PG: plasma glucose SMPG: Self-measured plasma glucose

**Figure 17-1 Novo Nordisk classification of hypoglycaemia**

**ADA classification of hypoglycaemia**

- Severe hypoglycaemia: An episode requiring assistance of another person to actively administer carbohydrate, glucagon, or take other corrective actions. PG concentrations may not be available during an event, but neurological recovery following the return of PG to normal is considered sufficient evidence that the event was induced by a low PG concentration.
- Asymptomatic hypoglycaemia: An episode not accompanied by typical symptoms of hypoglycaemia, but with a measured PG concentration  $\leq 3.9$  mmol/L (70 mg/dL).
- Documented symptomatic hypoglycaemia: An episode during which typical symptoms of hypoglycaemia are accompanied by a measured PG concentration  $\leq 3.9$  mmol/L (70 mg/dL).
- Pseudo-hypoglycaemia: An episode during which the person with diabetes reports any of the typical symptoms of hypoglycaemia with a measured PG concentration  $> 3.9$  mmol/L (70 mg/dL) but approaching that level.
- Probable symptomatic hypoglycaemia: An episode during which symptoms of hypoglycaemia are not accompanied by a PG determination but that was presumably caused by a PG concentration  $\leq 3.9$  mmol/L (70 mg/dL).

Note: Glucose measurements are performed with capillary blood calibrated to plasma equivalent glucose values

PG: plasma glucose SMPG: Self-measured plasma glucose

### Figure 17–2 ADA classification of hypoglycaemia

Treatment emergent hypoglycaemic episodes are presented in terms of the number of subjects with at least one event (N), the percentage of subjects with at least one event (%), the number of events

Protocol  
Trial ID: NN1218-4357  
UTN: U1111-1197-8289

**CONFIDENTIAL**

Date:  
Version:  
Status:  
Page:

30 November 2020  
5.0  
Final  
89 of 105

